10.3 Required at End of Treatment (4-6 weeks from last study treatment)

The following must be obtained at post-treatment visit (4-6 weeks from the last day of treatment).

- Medical history, medication review, physical exam, height and weight, ECOG performance status (see Appendix A)
- Toxicity assessment
- CBC with differential, blood chemistries including complete metabolic panel, phosphorus, magnesium, uric acid, LDH, TSH, creatinine kinase, lipase, triglycerides. Urine studies to include a urine dipstick for blood and protein and if positive (2+ or greater for protein) a microscopic urinalysis and 24 hour urine collection (for protein).
 - For patients assigned to cohorts A2, A3 and B2 with a previous history of anthracycline treatment and who are at high risk of cardiac failure (ie those that have New York Heart Association Class I heart failure), troponin I (troponin T is allowed if the assay utilized can be verified to have cardiac specificity) and Nterminal of the prohormone brain natriuretic peptide (Nt-proBNP) levels will be evaluated at the end of treatment visit
- Peripheral blood sample for biomarker studies
- Tumor restaging, which will consist of PET and CT scans, which may be a combined study; in the event of a complete response by imaging, a bone marrow biopsy will be necessary to confirm a complete response. MRIs may be used for patients in whom CT scans are contraindicated. Restaging will occur 4-6 weeks after the last dose of study therapy, then at 6, 12, and 18 months from the end of treatment (+/-2 weeks). CT scans (neck if involved at baseline, chest, abdomen, pelvis) may be done in place of PET scans for surveillance at the above timepoints following a complete response. For all complete responses by imaging, a bone marrow biopsy will be necessary as part of their restaging to confirm complete remission.
- Stool sample for biomarker testing
- EKG: Triplicate 12-lead EKGs will be done in patients in cohorts A2, A3, and B2 at the end of treatment visit.
- Echocardiogram (TTE) or multigated acquisition (MUGA) scan: TTE or MUGA scan should be performed at the end of treatment visit (if not performed within the preceding 3 months) for patients in cohorts A2, A3, and B2

10.4 Required during Follow-Up (every 3 months +/- 2 weeks from the end of treatment)

- Medical history, medication review, physical exam, height and weight, ECOG performance status (see Appendix A)
- Toxicity assessment
- CBC with differential, blood chemistries including complete metabolic panel, phosphorus, magnesium, uric acid, and LDH.
- Peripheral blood sample for biomarker studies at every other follow-up visit starting at 6 months (+/- 2 weeks) from the end of treatment until 24 months (+/- 2 weeks) from the end of treatment.
- Tumor restaging, which will consist of PET and CT scans, which can be a combined study, at month 6, 12, and 18 months from the end of therapy; in the event of a complete response by imaging, a bone marrow biopsy will be necessary to confirm a complete response. Also in the event of a complete response, PET scans need not be repeated and patients may be followed with CT scans of the chest, abdomen and pelvis (+/- neck if the neck was previously involved) with PO and IV contrast alone. MRIs may be used for patients in whom CT scans are contraindicated.
- Tumor biopsy at the time of progression
- After 2 years of follow up, patients will be followed only for relapse and survival with follow up in person or by phone call with the patient or the local physician every 6 months.

11. MEASUREMENT OF EFFECT

11.1 Disease Response Assessments

18F-fluorodeoxyglucose (18F-FDG) Positron Emission Tomography (PET) imaging will be used in conjunction with Computerized Tomography (CT) imaging to confirm a disease assessment of CR at the end of treatment. The screening 18F-FDG PET-CT imaging will be used to determine evaluable index lesions for each patient. For 18F-FDG PET-CT, tumor background ratios and development of new sites of abnormality will be recorded.

Results of the 18F-FDG PET studies will be scored according to methods developed by the American College of Radiology Imaging Network. All centers participating in the study will use the same 18F-FDG PET methodologies and measures, to the extent possible, and one center will be designated as the central lab to be used for final interpretation of 18F-FDG PET data.

Anti-cancer activity will be assessed at baseline, during treatment as specified in the Study Calendar, whenever disease progression is suspected (eg, symptomatic deterioration), at the time of withdrawal from treatment (if not performed in the previous 6 weeks) or at the end of treatment (4-6 weeks from the last dose of study therapy) and at follow-up visits 6, 12, and 18 months (+/- 2weeks) from the end of therapy or until disease progression.

If imaging is used in disease assessment, the same imaging technique (CT) used to characterize each identified and reported lesion at baseline will be employed in post-baseline disease assessments.

Assessment of response will be made using the Lugano 2014 criteria and LyRIC (Appendix D).

All patients' files and radiologic images and pathology samples must be available for source verification and for potential peer review.

For all patients who achieve a complete response (CR) by imaging, a bone marrow biopsy is necessary to confirm a complete remission.

11.1.1 Duration of Response

Duration of overall response: The duration of overall response is measured from the time measurement criteria are met for CR or PR (whichever is first recorded) until the first date that recurrent or progressive disease is objectively documented (taking as reference for progressive disease the smallest measurements recorded since the treatment started, or death due to any cause. Participants without events reported are censored at the last disease evaluation).

Duration of overall complete response: The duration of overall CR is measured from the time measurement criteria are first met for CR until the first date that progressive disease is objectively documented, or death due to any cause. Participants without events reported are censored at the last disease evaluation.

Duration of stable disease: Stable disease is measured from the start of the treatment until the criteria for progression are met, taking as reference the smallest measurements recorded since the treatment started, including the baseline measurements.

11.1.2 Progression-Free and Overall Survival

Overall Survival: Overall Survival (OS) is defined as the time from randomization (or registration) to death due to any cause, or censored at date last known alive.

Progression-Free Survival: Progression-Free Survival (PFS) is defined as the time from randomization (or registration) to the earlier of progression or death due to any cause. Participants alive without disease progression are censored at date of last disease evaluation.

Time to Progression: Time to Progression (TTP) is defined as the time from randomization (or registration) to progression, or censored at date of last disease evaluation for those without progression reported.

11.1.3 Response Review

For purposes of data analysis and reporting, responses on this trial will be centrally assessed through the Tumor Imaging Metrics Core at DF/HCC.

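### PFS and response duration count late events without limit but censor event-free patients at an undefined last disease evaluation; if that means the last scheduled scan, estimates beyond about 2 years are biased downward

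*Combined protocol and SAP*

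**What the plan says.** **Events.** In Section 11.1.2, PFS runs "to the earlier of progression or death due to any cause", with no cut-off tied to the last assessment. In Section 11.1.1, duration of overall response runs "until the first date that recurrent or progressive disease is objectively documented", or to death. CR duration is built the same way. Time to progression (TTP) in Section 11.1.2 runs "to progression, or censored at date of last disease evaluation for those without progression reported", so death is not a TTP event.

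**Censoring.** For PFS, "Participants alive without disease progression are censored at date of last disease evaluation". For response and CR duration, "Participants without events reported are censored at the last disease evaluation". OS, by contrast, is censored at the date the patient was last known to be alive.

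**Assessment schedule.** Section 11.1 places post-treatment assessments "at follow-up visits 6, 12, and 18 months (+/- 2weeks) from the end of therapy or until disease progression". Section 10.4 agrees: "Tumor restaging, which will consist of PET and CT scans, which can be a combined study, at month 6, 12, and 18 months". No later scan is scheduled, although Section 11.1 also calls for assessment whenever progression is suspected.

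**Follow-up after the scans.** Section 10.4 has clinic visits every 3 months, and then: "After 2 years of follow up, patients will be followed only for relapse and survival with follow up in person or by phone call", every 6 months. Section 5.5 says only that patients enter survival follow-up after 24 months.

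**Use.** PFS is a secondary objective (Section 1.3) and is called a key secondary endpoint in Section 1.1. The only PFS time point named in Section 13.1 is 2 years. Study completion is expected at 48 months (Section 13.2), and Section 14 holds the first analysis until all patients have reached the End of Study visit or gone off study.

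**The concern.** Kaplan-Meier estimation needs events and non-events to be observed under the same rule. Here a relapse found at month 36 is an event at month 36. A patient found relapse-free at the same contact is, if evaluation means scan, censored back at about month 23-25. Event-free patients therefore leave the risk set together at the last scan, and those who remain are selected because they will have an event.

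Several small cohorts are being compared informally in an indolent disease, with follow-up running well past the last scan. A PFS or response-duration curve that drops towards zero for this reason could make a combination look less durable than it is.

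**Working it through.** The plan gives no sample size, event count or precision for PFS, TTP or response duration, so there is no figure of its own to reproduce.

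**1. When the last scheduled scan falls (months of 30.44 days from first dose on day -6).**
- Cycle 6 day 15 is 7 + 5 × 28 + 14 = 161 days after first dose, or 5.3 months. Adding 18 gives 23.3.
- The end of cycle 6 is 7 + 6 × 28 = 175 days, or 5.75 months (the 25 weeks of Section 5.4). Adding 18 gives 23.8.
- The end-of-treatment visit, 4-6 weeks after the last dose, is at 189-203 days, or 6.2-6.7 months. Adding 18 gives 24.2-24.7.
- With the ±2-week window (0.46 months), the range is 22.8-25.1.

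Response duration starts at first response, so its break point comes earlier, at about 18-21 months on its own clock.

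**2. A hand example without a model.** Take 15 patients, 7 with events by the last scan and 8 event-free, 2 of whom relapse later.
- At the last scan, KM = 8/15 = 0.53.
- Censored at the scan: 6 patients leave and 2 remain at risk. KM goes to 0.53 × 1/2 = 0.27, then to 0.
- Censored at later contacts (after both relapses): KM = 8/15 × 7/8 × 6/7 = 6/15 = 0.40, the proportion who never had an event.

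**3. Simulation.** From the documents: 15 patients per cohort, 24-month accrual, data cut at 48 months, and the scan times above. Assumed: uniform accrual, exponential PFS, scan-detected events dated at the scan, all later events captured and dated when they occur, treatment starting at registration, and no off-schedule evaluations in event-free patients. Under exponential PFS, true S(36) = S(24)^1.5.

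Mean KM estimate at 36 months, with the last scan at 23.3 / 24.4 months:

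| True 24-month PFS | True 36-month PFS | Late events counted, censor at last scan | Late events counted, censor at 6-monthly contact | Late events ignored, censor at last scan |
|---|---|---|---|---|
| 50% | 0.35 | 0.13 / 0.14 | 0.33 / 0.33 | 0.51 / 0.49 (flat) |
| 70% | 0.59 | 0.23 / 0.26 | 0.56 / 0.57 | 0.71 / 0.70 (flat) |

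At a true 50% with the last scan at 24.4 months, the first rule gives a KM of exactly zero in 53% of cohorts by 36 months and 80% by 42 months. Under contact censoring these are 3% and 13%.

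**4. How far this depends on the reading** (true 24-month PFS 60%, true 36-month PFS 0.6^1.5 = 0.46, follow-up 24-48 months, last scan at 23.3 months):
- scan only: 0.17
- clinic visits count, so censoring moves to about 30 months: 0.32-0.33, with no bias at 30 months
- 6-monthly relapse contacts count: 0.45, essentially unbiased
- scan only, but just 20% of late events captured: 0.44. The average is near the truth because many cohorts then have no late event and stay flat. A cohort that does have one is still pulled down.

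**5. Two-year PFS.** With the last scan at 23.3 months, scan censoring against contact censoring gives 0.475 against 0.496 (true 50%) and 0.672 against 0.699 (true 70%). The difference is 1-4 points over the range examined. With the last scan at 24.4 months the two rules agree to 0.001 (0.584 against 0.585; 0.760 against 0.761).

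**The case against.** **The scan is a reading, not a definition.** The text says disease evaluation, and Section 11.1 refers to imaging conditionally. Visits with history and examination are scheduled through 24 months, followed by contacts specifically about relapse. If those contacts are evaluations, the problem disappears. This stands, and it is why the size is conditional. The scan is still the natural reading: the routine schedule in Section 11.1 ends at 18 months, response is judged by Lugano and LyRIC with central imaging review, and Section 11.1.2 itself separates last known alive (OS) from last disease evaluation (PFS).

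**Late relapse capture is not settled.** Section 5.5 mentions only survival follow-up after 24 months, while Section 10.4 includes relapse. This stands. Deaths would be collected under either.

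**Stronger readings the documents do not support.**
- A reader might infer that the curves will certainly collapse. That needs the scan reading, captured late events and no later evaluations in event-free patients.
- A reader might infer that PFS, TTP and response duration suffer alike. TTP does not count deaths, so only late relapses affect it. Response duration requires objective documentation, so a relapse known only by telephone may not count; deaths and documented relapses do.
- A reader might infer that every planned median is wrong. No median or 36-month estimate is named, and 2-year PFS hardly moves.

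**A relapse-free telephone call does not apply the response criteria.** Censoring there could miss progression and bias PFS upward. This is fair, and it bears on which version should be primary.

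**Conclusion.** The concern holds in a limited form. Events have no time limit, censoring goes back to an undefined last evaluation, and scheduled evaluations stop at about 23-25 months while follow-up continues. If evaluation means the last scheduled scan, PFS and response-duration estimates beyond it are biased downward: 36-month PFS averages about 0.13-0.26 against a true 0.35-0.59, under exponential PFS, n = 15, full capture of late events and a true 24-month PFS of 50-70%. Those conditions are assumptions, not document figures.

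The average bias is smaller if clinic visits count or few late events are captured, and absent if the 6-monthly contacts count. Neither primary endpoint (RP2D, CR rate) nor any opening, stopping or success rule uses these measures. It should be corrected before the time-to-event analyses, but it does not threaten the trial's main conclusions.

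**What to change.** 1. In Sections 11.1.1 and 11.1.2, define disease evaluation and say whether clinic visits and the 6-monthly relapse contacts qualify.
2. Apply one observation rule to events and censoring. Either (a) count only events within one scan interval (6 months) of the last evaluation, and report no curves or medians past the last scheduled evaluation; or (b) censor at the last contact at which progression status was documented. Report the other as a sensitivity analysis. Option (a) stays closer to Lugano and LyRIC and is the safer primary. Its two parts belong together, because the event limit alone leaves the asymmetry in place for that interval.
3. Reconcile Section 5.5 with Section 10.4 on whether relapse is collected after 24 months. Option (b) depends on the answer.

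The cost is wording. No added scan is needed, and no added visit if Section 10.4 stands. Option (a) gives up late follow-up; option (b) relies on weaker evidence than a scan.

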12. DATA REPORTING / REGULATORY REQUIREMENTS

Adverse event lists, guidelines, and instructions for AE reporting can be found in Section 7.0 (Adverse Events: List and Reporting Requirements).

12.1 Data Reporting

12.1.1 Method

The Office of Data Quality (ODQ) will collect, manage, and perform quality checks on the data for this study.

12.1.2 Responsibility for Data Submission

Investigative sites are responsible for submitting data and/or data forms to the Office of Data Quality (ODQ) in accordance with DF/HCC policies.

12.2 Data Safety Monitoring

The DF/HCC Data and Safety Monitoring Committee (DSMC) will review and monitor toxicity and accrual data from this study. The committee is composed of medical oncologists, research nurses, pharmacists and biostatisticians with direct experience in cancer clinical research. Information that raises any questions about participant safety will be addressed with the Overall PI and study team.

The DSMC will review each protocol up to four times a year with the frequency determined by the outcome of previous reviews. Information to be provided to the committee may include: up-to-date participant accrual; current dose level information; DLT information; all grade 2 or higher unexpected adverse events that have been reported; summary of all deaths occurring within 30 days of intervention for Phase I or II protocols; for gene therapy protocols, summary of all deaths while being treated and during active follow-up; any response information; audit results, and a summary provided by the study team. Other information (e.g. scans, laboratory values) will be provided upon request.

12.3 Multi-Center Guidelines

This protocol will adhere to the policies and requirements of the DF/HCC Multi-Center Data and Safety Monitoring Plan. The specific responsibilities of the Overall PI, Coordinating Center, and Participating Institutions and the procedures for auditing are presented in Appendix C.

- The Overall PI/Coordinating Center is responsible for distributing all IND Action Letters or Safety Reports to all participating institutions for submission to their individual IRBs for action as required.
- Mechanisms will be in place to ensure quality assurance, protocol compliance, and adverse event reporting at each site.

• Except in very unusual circumstances, each participating institution will order the study agent(s) directly from supplier. A participating site may order the agent(s) only after the initial IRB approval for the site has been forwarded to the Coordinating Center.

13. STATISTICAL CONSIDERATIONS

This is an open-label, phase 1b clinical trial of immunotherapy in combination with rituximab in patients with both relapsed/refractory or previously untreated follicular lymphoma.

13.1 Study Design/Endpoints

Primary endpoints:

- Determine the RP2D of these immunotherapy combinations for further testing
- Complete response rate using 2014 Lugano criteria

Secondary endpoints:

- Efficacy as measured by the objective, complete and partial response, stable disease and progressive disease rates by 2014 Lugano and LyRIC criteria, rate of MRD negativity at 6 and 12 months, 2-year progression free survival (by 2014 Lugano and LyRIC), overall survival and time to next treatment response duration
- Safety categorized by the rate of:
 - Grade 3 and higher toxicities, both regardless of attribution, and at least possibly attributed to the study treatment
 - Grade 2 or higher toxicity at least probably related to study treatment.
 - Adverse events leading to discontinuation due to toxicity.

Correlative or exploratory endpoints (when possible):

- Correlation between overall and complete response rates and MRD negativity and histologic grade (1-2 versus 3A) and FLIPI
- Calculation of the m7-FLIPI and correlation with overall and complete response rate and MRD negativity
- Comparisons of the tumor microenvironment composition and gene expression pre- and on-treatment
- Comparisons of the composition of the circulating immune environment, including the T cell repertoire, in the peripheral blood pre- and on-treatment
- Exploration of genetic markers of tumor response or resistance to therapy through whole exome sequencing
- Correlation between fecal microbiome and response or resistance to therapy

All exploratory or correlative endpoints will be analyzed descriptively.

13.2 Sample Size, Accrual Rate and Study Duration

13.2.1 Determining RP2D

The Dose Escalation phase of this study follows a 3+3 design with 2 or 3 dose levels for each cohort to determine the RP2D for each drug combination being tested. The RP2D will be defined as the highest dose level for which there are no more than 1/6 DLTs observed.

The following table shows the probability of escalation under various true DLT rates. With this design there is 91% probability of dose escalation if the true rate of DLT is 10% and 8% probability of escalation if the true DLT rate is 60%.

True Rate of DLT	Probability of escalation
10%	0.91
20%	0.71
30%	0.49
40%	0.31
50%	0.17
60%	0.08

Dose Expansion

Once the RP2D is established for a given cohort/drug combination in the relapsed/refractory setting (part A), an additional 9 or 12 eligible patients will be treated at the RP2D, for a total of 15 patients treated at that dose level. Whether it is 9 or 12 is dependent on whether 6 or 3 patients were treated at that dose level to determine the RP2D, respectively. With 15 patients, the 90% confidence interval for DLT will be no wider than +/-23%.

A combination will be judged promising in terms of efficacy **in part A (relapsed/refractory setting)** if in addition to being tolerable 3 or more patients out of 15 obtain a CR (based on a null hypothesis of CRR 5% and alternative hypothesis of CRR 30% with 87% power and a 4% one sided type I error).

True but unknown CR rate	0.05	0.1	0.15	0.2	0.25	0.3
Prob of observing ≥ 3 CRs	0.04	0.18	0.40	0.60	0.76	0.87

In the **relapsed/refractory setting (part A)**, a particular combination (A1b, A2b, A3b) will be judged tolerably safe if 3 or fewer patients out of 15 experience a DLT (based on a null hypothesis for DLT rate of 40% and an alternative hypothesis of 10% with 94% power and a 9% one-sided type I error).

True but unknown prob. of excessive toxicity	0.05	0.1	0.15	0.2	0.25	0.3	0.35	0.4
Prob of observing ≤3 pts with excessive tox	0.99	0.94	0.82	0.65	0.46	0.30	0.15	0.09

If a cohort in part A meets these efficacy and toxicity endpoints, it will open in cohort B in previously untreated FL patients. These cohorts will treat up to 15 patients each. A combination will be judged promising in terms of efficacy **in part B (previously untreated setting)** if in addition to being tolerable based on above criteria) if 6 or more patients out of 15 obtain a CR (based on a null hypothesis of CRR 20% and alternative hypothesis of CRR 50% with 85% power and a 6% one sided type I error).

True but unknown CR rate	0.2	0.25	0.3	0.35	0.4	0.5
Prob of observing \ge 6 CRs	0.06	0.15	0.28	0.44	0.60	0.85

In the **upfront setting (part B)**, a particular combination (B1, B2) will be judged safe if 2 or fewer patients out of 15 experience excessive toxicity as defined above (based on a null hypothesis for excessive toxicity rate of 35% and an alternative hypothesis of 10% with 82% power and a 6% one-sided type I error).

True but unknown prob. of excessive toxicity	0.05	0.1	0.15	0.2	0.25	0.3	0.35
Prob of observing ≤2 pts with excessive tox	0.96	0.82	0.60	0.40	0.24	0.13	0.06

Based on historical rates, anticipated accrual will be 24 months. The anticipated time to primary endpoint is 30 months, and to study completion 48 months.

